#### 3.7.1.2 *Immunogenicity analyses*

Dupilumab anti-drug antibody (ADA) status (negative or titer value, if positive in the ADA assay) at Visit 2 (Day 1), Week 12, Week 24, Week 52 and EOS visit will be provided. Given the variable treatment period, the EOS visit may be between 36 to 64 weeks. The neutralizing antibody results for ADA positive samples will be provided.

Incidence will be provided for the following ADA response categories. Treatment-emergent and treatment-boosted response will be defined based on samples collected in the on-treatment period.

Pre-existing immunoreactivity is defined as:

An ADA positive response in the assay at baseline with all post first dose ADA results negative, OR an ADA positive response at baseline with all post first dose ADA responses less than 4-fold over baseline titer levels.

Treatment-emergent ADA responses are defined as:

A positive response in the ADA assay post first dose, when baseline results are negative or missing.

Treatment-emergent ADA responses are further classified as persistent, indeterminate or transient

- a) Persistent response - defined as a treatment-emergent ADA response with two or more consecutive ADA positive sampling time points, separated by greater than ( $>$ ) 12-week period (84 days), with no ADA negative samples in between.
- b) Indeterminate response - defined as a treatment-emergent response with only the last collected sample positive in the ADA assay

c)

Treatment-boosted response is defined as:

The following summary will be provided based on ADA population:

- Number (%) of participants with pre-existing immunoreactivity
- Number (%) of participants with treatment-emergent ADA
- The summary statistics (including number, median, Q1, Q3, minimum and maximum) of the peak post-baseline titer for participants with treatment-emergent ADA, and participants with persistent, indeterminate and transient ADA response
- Number (%) of participant with transient treatment-emergent ADA
- Number (%) of participants with persistent treatment-emergent ADA
- Number (%) of participants with indeterminate treatment-emergent ADA
- Number (%) of participants with treatment-boosted ADA
- The summary statistics (including number, median, Q1, Q3, minimum and maximum) of the peak post-baseline titer for participants with treatment-boosted ADA
- The summary statistics (including number, mean, SD, median, Q1, Q3, minimum and maximum) of the ratio of peak post-baseline titer to baseline titer for participants with treatment-boosted ADA
- Listing of ADA peak titer levels and neutralizing antibody status
- Number (%) of participants with neutralizing antibody status

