- c Participants who discontinue the study treatment prematurely (prior to completing Week 24 of treatment period) will perform the end of treatment (EOT) assessments at the time of discontinuation to assure a complete clinical assessment in close temporal proximity to the premature termination of study treatment. In addition, to allow assessment of participant outcomes over the stipulated study period, participants will be asked and encouraged to complete all remaining study visits and participate in all assessments according to the visit schedule.
- d Consent to be obtained for optional procedures (whole blood DNA, whole blood RNA sampling, and serum/plasma sampling for archival; human immunodeficiency virus (HIV) test if specific consent locally required).
- e Past medical history including allergic comorbidities (asthma, aspirin sensitivity, allergic rhinitis etc). Surgeries will be assessed including type and dates of sinonasal surgeries in the past. Systemic corticosteroids (SCS) use (number of courses, doses, way of administration and duration) in the past 2 years before V1 and/or contraindication/intolerance to SCS, as well as long-term antibiotics use (>2 weeks) in the previous year will be entered in the electronic case report form (eCRF).
- f Details on actual or planned date for surgery type and outcome (whenever possible) of surgery will be recorded in a specific eCRF page. If surgery is performed during the study treatment period or follow-up an adverse event (AE) or serious adverse event (SAE) page will be completed. Participants will be discontinued from study treatment and assessed as soon as possible using the procedures normally planned for the EOT Visit. If surgery is scheduled after the planned end of study, a follow-up contact(s) may be required to document the surgery date and outcome.
- g Nasal endoscopy: Endoscopy (including use of decongestants before the procedure) will be performed at Screening Visit only for eligibility confirmation. At V2, Investigator will review V1 results from central reader to confirm entry criteria and reconfirm eligibility based on review of inclusion/exclusion criteria.

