### **7.1.2 Temporary discontinuation**

Temporary intervention discontinuation may be considered by the Investigator because of suspected AEs. For all temporary intervention discontinuations, duration should be recorded by the Investigator in the appropriate pages of the eCRF.

Temporary intervention discontinuation decided by the Investigator corresponds to at least 1 dose not administered to the participant. Following a temporary interruption or missed dose, the study intervention should be reinitiated at the next scheduled administration, maintaining the planned dose.

If 2 consecutive IMP doses have been missed, the study intervention will be definitively discontinued (see [Section 7.1.1](#)). Investigator must contact the participant to instruct not to take any subsequent injection.

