**Table 3 - Populations for analyses**

Population	Description
Screened	All participants who sign the informed consent form.
Randomized	The randomized population includes all participants with a treatment kit number allocated and recorded in the IRT database, and regardless of whether the treatment kit was used or not. Participants treated without being randomized will not be considered randomized and will not be included in any efficacy population.
Intent-to-treat (ITT)	All randomized participants analyzed according to the treatment group allocated by randomization regardless if treatment kit is used or not.
ITT with screening blood eosinophil count $\geq 300$ cells/mm $^3$	All randomized participants with screening blood eosinophil count $\geq 300$ cells/mm $^3$ analyzed according to the treatment group allocated by randomization regardless if treatment kit is used or not.
ITT with screening blood eosinophil count $< 300$ cells/mm $^3$	All randomized participants with screening blood eosinophil count $< 300$ cells/mm $^3$ analyzed according to the treatment group allocated by randomization regardless if treatment kit is used or not.
Safety	All participants randomly assigned to study intervention and who take at least 1 dose of study intervention. Participants will be analyzed according to the intervention they actually received. Randomized participants for whom it is unclear whether they took the study medication will be included in the safety population as randomized. For participants who accidentally receive different study intervention from the planned, the actual intervention allocation for as-treated analysis will be the dupilumab group.
Pharmacokinetic (PK)	The PK population includes all participants in the safety population with at least 1 non-missing result for functional dupilumab concentration in serum after the first dose of the study intervention. Participants will be analyzed according to the intervention actually received.
Anti-drug antibody (ADA)	ADA population includes all participants in the safety population who have at least 1 non-missing result in the ADA assay after the first dose of the study intervention. Participants will be analyzed according to the intervention actually received.

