#### *Observation period*

The observation period will be divided into 4 segments:

- The **pre-treatment period** is defined as the period up to the first IMP administration.
- The **treatment-emergent (TE) period** is defined as the period from the first IMP administration to the last IMP administration + 98 days. The treatment-emergent period includes the following 2 periods:
  - The **on-treatment period** is defined as the period from the first IMP administration to the last administration of the IMP + 14 days
  - The **residual treatment period** is defined as the period from the end of the on-treatment period to the end of the treatment-emergent period.
- The **post-treatment period** is defined as the period after the end of the treatment-emergent period.

The on-study observation period is defined as the time from the first IMP until the end of the study defined as the last scheduled visit for those who completed the study and the end-of-study date

collected on electronic case report form (e-CRF) page “Completion of End of Study/Follow-up” for those who did not complete the study. If death is the end-of-study reason, date of death will be used.

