### ***3.7.1.2.1 Association of Immunogenicity with Exposure, Safety and Efficacy***

The safety and efficacy analysis mentioned below will be conducted using the following categories:

ADA positive participants: Participants with treatment-emergent or treatment-boosted response.

ADA negative participants: Participants with pre-existing immunoreactivity or negative in the ADA assay at all time points.

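### Treatment-emergent ADA counts samples only to last dose + 14 days, the planned EOT sample day, so a later first positive is neither 'ADA positive' nor 'ADA negative'; the samples behind 'persistent' are unstated

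*SAP*

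**What the plan says.** SAP 3.7.1.2 sets the restriction: "Treatment-emergent and treatment-boosted response will be defined based on samples collected in the on-treatment period". SAP 3.1 (Observation period) runs the on-treatment period from the "first IMP administration to the last administration of the IMP + 14 days". The same section defines a longer treatment-emergent period, to last dose + 98 days, but ADA does not use it.

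Four other ADA definitions are not written with that limit:

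- The base definition of treatment-emergent ADA (SAP 3.7.1.2): "A positive response in the ADA assay post first dose, when baseline results are negative or missing".
- Pre-existing immunoreactivity (SAP 3.7.1.2) needs a positive baseline and then looks at every result after the first dose.
- The ADA population (SAP Table 3) takes safety-population participants with "at least 1 non-missing result in the ADA assay after the first dose of the study intervention".
- 'ADA negative' (SAP 3.7.1.2.1) means "Participants with pre-existing immunoreactivity or negative in the ADA assay at all time points". 'ADA positive' means treatment-emergent or treatment-boosted.

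A treatment-emergent response is persistent if consecutive positives are separated by more than a "12-week period (84 days), with no ADA negative samples in between". It is indeterminate if only the last collected sample is positive.

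On sampling, SAP 3.7.1.2 reports ADA at Day 1, Weeks 12, 24 and 52, and EOS. Protocol 6.1 places the last dose between Week 22 and Week 50. Protocol 1.3 allows 3 days either side for doses and for visits up to EOT. After premature discontinuation, footnote c of Protocol 1.3 says "participants will be asked and encouraged to complete all remaining study visits and participate in all assessments according to the visit schedule". Protocol 7.1.2 adds: "If 2 consecutive IMP doses have been missed, the study intervention will be definitively discontinued".

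**The concern.** Incidence of treatment-emergent ADA over time is a secondary endpoint (Protocol 3; SAP Table 1). The numerator stops at last dose + 14 days, while the denominator and the negative category have no such stop. If the cut-off falls on the day of the last planned on-treatment sample, ordinary visit timing decides whether that sample counts. A positive after the cut-off then leaves the participant without a category.

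The persistence threshold raises a related question. It equals the planned interval between the two main on-treatment samples, and it is a strict inequality. For someone whose treatment ends near Week 24, the label could turn on a visit being one day early or late.

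**Working it through.** **Inputs.** Study day = 7 × week + 1. The plan's own figures reproduce: 12 weeks × 7 = 84 days, and Weeks 12, 24 and 52 are Days 85, 169 and 365, the target days in SAP Table 11.

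**Cut-off against the EOT sample.**

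- Last dose Week 22 = Day 155; 155 + 14 = 169 = Week 24.
- Last dose Week 50 = Day 351; 351 + 14 = 365 = Week 52.

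There is no slack at either end of the range. After a last dose given on its nominal day, an EOT visit 1 to 3 days late is within window but excluded. With dose and visit each within 3 days of nominal, the gap runs from 166 − 158 = 8 to 172 − 152 = 20 days, and 15 to 20 days is excluded. Of the 7 × 7 = 49 day combinations, 7 give exactly 14 days and (49 − 7)/2 = 21 give more. This counts combinations; it does not predict how visits will fall.

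**Cut-off against post-discontinuation samples (planned schedule).**

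- The Week 12 sample counts if 85 ≤ last dose + 14, so the last dose must be Day 71 (Week 10) or later.
- The Week 24 sample counts if 169 ≤ last dose + 14, so the last dose must be Day 155 (Week 22) or later.
- After withdrawal for two missed doses, the EOT sample is at least 28 days after the last dose and never counts.
- So, after such a withdrawal with a last dose at Weeks 0 to 8, no planned post-baseline ADA sample counts. With a last dose at Weeks 10 to 20, only Week 12 counts.
- If only the Week 22 dose is missed by a participant stopping at Week 24, the last dose is Week 20 = Day 141. Then 169 − 141 = 28 days, 14 past the cut-off.

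**Classification.** Take a participant negative at baseline and in every on-treatment sample, whose first positive comes after the cut-off.

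- ADA population: yes, because there is a post-first-dose result.
- 'ADA positive': no, because no on-treatment sample is positive.
- 'ADA negative': no. Pre-existing immunoreactivity needs a positive baseline, and the participant is not negative throughout.

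The gap does not need an EOS sample; a late EOT or post-discontinuation sample is enough.

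**Persistence.** Week 12 to Week 24 is 169 − 85 = 84 days, which is not more than 84. In window, the gap runs from 166 − 88 = 78 to 172 − 82 = 90 days. The same count applies: 21 of 49 combinations exceed 84. If only on-treatment samples count, an on-schedule participant stopping at Week 24 is not persistent. Nor is that participant indeterminate, because two samples are positive.

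Longer treatment changes this. Week 24 to Week 52 is 365 − 169 = 196 days. Measured from first to last positive, Week 12 to an EOT at Week 30 is 211 − 85 = 126 days.

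If EOS samples count, positives at Weeks 12, 24 and 36 span 253 − 85 = 168 days and would qualify when measured first to last. Week 24 and EOS alone (253 − 169 = 84) would not.

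**The case against.** The strongest reply is that the on-treatment limit is a choice. SAP 3.1 defines both a 14-day and a 98-day period, and SAP 3.7.1.2 picks the first, so the sentence can be read as narrowing the post-first-dose definition. That stands: a reader might infer that the cut-off is itself a mistake, and the documents do not show that. The choice still leaves the population and the negative category on a wider set of samples.

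A reader might also infer that Week 12 and Week 24 positives can never be persistent in someone stopping at Week 24. The documents do not support this unconditionally. The on-treatment sentence names treatment-emergent and boosted status; the sub-class definitions refer to sampling time points and the last collected sample, with no stated limit. The transient and boosted definitions are blank in the public copy, so the final label for a participant positive only at Weeks 12 and 24 is unknown.

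The group is also small by design. Treatment stops for everyone when the last participant completes 24 weeks (SAP 1.1), so someone randomized k weeks before the last participant is treated for about 24 + k weeks, up to 52. For most, the Week 24 sample is mid-treatment.

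Nor should the Week 24 window in SAP Table 11, which runs to Day 266, be set against Day 169 as a conflict. That window serves by-visit summaries, while the cut-off depends on each participant's own last dose.

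Finally, late positives stay visible, because ADA status and titer are reported by visit. The ADA associations with efficacy and safety are optional, and no hypothesis is tested.

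**Conclusion.** The point holds as a minor one. The firm part is the cut-off: it falls on the planned EOT sample day, it excludes some samples the protocol plans to collect, and the ADA categories are not exhaustive. This rests only on the SAP wording and day counts.

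The persistence part is conditional. It applies if the on-treatment limit carries into the persistent/indeterminate split, and only to participants stopping at or near Week 24. Few are expected to stop at exactly Week 24, and those treated longer can still qualify.

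The size cannot be computed, because the documents give no ADA rate, discontinuation pattern or count stopping near Week 24. It is probably small. For the cut-off it is zero if EOT samples are on time and no post-discontinuation sample is positive.

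Whether EOS samples add to the unclassified group is open. The SAP reports ADA at EOS, but the ADA row of the Schedule of Activities, as extracted, marks none. Because that table may be damaged in extraction, this is a matter to reconcile; it does not show that EOS samples were not planned.

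**What to change.** - Use one ADA observation period for all ADA categories, including every in-window EOT sample and post-discontinuation samples. All post-first-dose samples would do this, and would make 'ADA positive' and 'ADA negative' exhaustive and consistent with the ADA population. The SAP's 98-day period would reach an on-schedule EOS visit (155 + 98 = 253, Week 36; 351 + 98 = 449, Week 64) but not one 1 to 5 days late within its window.
- Define persistence as positives at nominal visits at least 12 weeks apart with no negative sample between. Relaxing the inequality to at least 84 days is not enough, because the in-window gap starts at 78.
- State whether EOS samples count towards the sub-classes, and reconcile EOS ADA sampling between SAP 3.7.1.2 and the Schedule of Activities.

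The cost is SAP wording and a programming rule, plus a Schedule of Activities alignment if EOS sampling is confirmed. No new data are needed. Reported ADA incidence and persistence may rise slightly.

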### **Kinetics of treatment-emergent ADA response**

Number (%) of participants with treatment-emergent ADA positive response at each visit will be summarized by each intervention group.

Plot of percentage of participants with treatment-emergent ADA positive response at each visit will be provided by each intervention group.

### ***3.7.1.2.1 Association of Immunogenicity with Exposure, Safety and Efficacy***

The safety and efficacy analysis mentioned below will be conducted using the following categories:

ADA positive participants: Participants with treatment-emergent or treatment-boosted response.

ADA negative participants: Participants with pre-existing immunoreactivity or negative in the ADA assay at all time points.

#### **Impact of ADA on PK profile**

Potential associations between ADA variables (eg, ADA peak titers, neutralizing antibody status, treatment-emergent, persistent, indeterminate and transient response, treatment-boosted) and impact on serum concentration profile of dupilumab may be explored. Plot of serum concentration of functional dupilumab versus visit will be provided by ADA variables for each dupilumab dose group. Individual participant plots of dupilumab concentration according to ADA status will be provided.

#### **Impact of ADA on clinical efficacy endpoints**

Associations between the ADA variables (eg, ADA peak titers, neutralizing antibody status, treatment-emergent, persistent, treatment-boosted) and the primary efficacy endpoint may be explored for the dupilumab dosed group.

#### **Association of ADA with clinical safety endpoints**

Association of safety versus ADA status may be analyzed in the ADA population. The safety assessment may focus on the following events:

- Severe injection site reactions last longer than 24 hours or serious injection site reactions
- Hypersensitivity reactions (SMQ (20000214) hypersensitivity narrow search confirmed by medical review)
- Anaphylactic reactions (SMQ (20000021) anaphylactic reaction narrow search)

### ***3.7.1.3 Biomarker analyses***

Blood, urine, nasal secretions and nasal brushing biomarkers will be summarized on the safety population. Baseline values will be the last value collected prior to the first IMP. Descriptive statistics (including number, mean, SD, median, Q1, Q3, min, max) of biomarkers at baseline and each post-baseline visit will be summarized.

Summary plots at each visit (mean, mean change from baseline and median percent change from baseline) will be provided for each biomarker by intervention group.

### 3.7.1.4 Health care resource utilization and productivity

The cumulative number of health care resource utilization and cumulative number of missed days of school/work will be summarized over the treatment period. Descriptive statistics (number of participants, mean, SD, median, minimum and maximum) will be provided.

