ACQ-6: Asthma Control Questionnaire 6-question version, ADA: anti-drug antibody, AE: adverse event, AESI: adverse event of special interest, CRSsNP: chronic rhinosinusitis without nasal polyposis, CT: computerized tomography, COVID-19: Coronavirus Disease 2019, D: day, DBP: diastolic blood pressure, ECG: electrocardiogram, eCRF: electronic case report form, EOS: end of study, EOT: end of treatment, EQ-5D-5L: 5-level version of the EuroQol 5 dimensions European quality of life-5D scale, FEF: forced expiratory flow, FEV1: forced expiratory volume, FVC: forced vital capacity, HBcAb: hepatitis B core antibody, HBsAb: hepatitis B surface antibody, HBsAg: hepatitis B surface antigen, HBV: hepatitis B virus, HCRU/P: Healthcare Resource Utilization/Productivity, HCV: hepatitis C virus, HCVAb: hepatitis C virus antibodies, HIV: Human Immunodeficiency Virus, IEC: independent ethics committee, Ig: immunoglobulin, IRB: institutional review board, IMP: investigational medicinal product, IRT: interactive response technology, INCS: intranasal corticosteroids, LABA: long-acting beta-agonists; LAMA: long-acting muscarinic acetylcholine, LTE4: leukotriene 4, PGDM: prostaglandin D2 metabolite, PGIS: patient global impression of severity, PGIC: patient global impression of change, PK: pharmacokinetic, PRO: patient-reported outcome, q2w: every 2 weeks, SAE: serious adverse event, SBP: systolic blood pressure, SC: Subcutaneous, SCS: systemic corticosteroids, sTSS: sinus Total Symptom Score, SNOT-22: Sino-Nasal Outcome Test – 22 item, TB: tuberculosis, TARC: thymus-and activation-regulated chemokine, UPSIT: University of Pennsylvania smell identification test, VAS: visual analog scale, V: Visit, W: week, WOCBP: women of childbearing potential.

- a The treatment period will be variable between 24 to 52 weeks; therefore, follow up may be between 36 to 64 weeks. V6 and V7 are optional for participants given variable treatment period.
- b All assessments at Randomization Visit (V2) are to be conducted pre-IMP dose with the exception of the assessment of local tolerability of subcutaneous (SC) injections.

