## 4 STUDY DESIGN

### 4.1 OVERALL DESIGN

This is a Phase 2 multicenter study to evaluate the efficacy and safety of dupilumab, in participants with uncontrolled CRSsNP. This is a randomized, double-blind, placebo-controlled study in adult participants regardless of screening eosinophil count to evaluate the treatment effect of dupilumab on sinus opacification as assessed by the LMK sinus CT scan total score and to provide data on safety.

All participants (adults only) will enter a screening period (2 to 4 weeks), with a 24 to 52-week treatment period, followed by post-treatment follow-up (12 weeks).

Approximately 70 adult participants will be randomized 1:1 (approximately 35 participants per arm) into 2 treatment groups as follows:

- Arm A: Dupilumab 300 mg q2w,
- Arm B: Matching placebo.

Randomization will be stratified by screening blood eosinophil count ( $\geq 300$  cells/mm $^3$  or  $< 300$  cells/mm $^3$ ), background INCS use (yes or no) and region.

To ensure enrollment according to the intended distribution of screening blood eosinophil count, alerts will be built into the IRT to control the number of participants in each stratification group as follows:

- $\geq 300$  cells/mm $^3$ : approximately 15 participants per arm,
- $< 300$  cells/mm $^3$ : approximately 20 participants per arm.

*Note: The treatment will stop for all participants when the LPI has completed 24 weeks of treatment. Therefore, all participants following Amendment 02 will be treated for at least 24 weeks and the other participants (enrolled before Amendment 02) will have variable treatment period and may continue up to 52 weeks.*

In addition, in order to have an adequate number of participants with comorbid asthma, alerts will be built into the IRT to limit the number of participants without comorbid asthma to no more than 70% of the randomized population.

During the study, participants who report deterioration requiring medical/surgical intervention may come to the site for clinical evaluation. An unscheduled visit may be used for this purpose and, if necessary, the Investigator may consider one of the treatment alternatives described in [Section 6](#).

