### WORK

*Please do not include workdays missed due to participation in this study, or for health conditions other than CRSsNP.*

4. Since the last assessment of HCRU (about four months back), how many days did this patient miss from work because of his/her chronic rhinosinusitis?

\_\_\_\_\_ days (half a day = 0.5 days)

5. Since the last assessment of HCRU (about four months back), how many days did this patient work while being bothered by his/her chronic rhinosinusitis?

\_\_\_\_\_ days (half a day = 0.5 days)

6. Since the last assessment of HCRU (about four months back), how much did this patient's chronic rhinosinusitis impact his/her performance in his/her work?

Please enter a number between 0 and 10, where 0 equals "not impacted", and 10 equals "extremely impacted".

\_\_\_\_\_ (score range 0 (not impacted) to 10 (extremely impacted))

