## VERSION HISTORY

This Statistical Analysis Plan (SAP) for study EFC16723 is based on the protocol dated 23-Feb-2023 (amended protocol 02).

The first participant was randomized on 24-Feb-2021.

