## 1 INTRODUCTION

### 1.1 STUDY DESIGN

This is a Phase 2, randomized, double-blind, placebo-controlled study to evaluate the efficacy and safety of dupilumab in adult participants with uncontrolled chronic rhinosinusitis without nasal polyposis (CRSsNP).

After a screening period of 2 to 4 weeks, approximately 70 participants will be centrally randomized (using permuted block randomization schedule) via Interactive Response Technology (IRT) in a 1:1 ratio to dupilumab 300 mg q2w or placebo. Randomization will be stratified by screening blood eosinophil count ( $\geq 300$  cells/mm $^3$  or  $< 300$  cells/mm $^3$ ), background intranasal corticosteroids (INCS) use (yes or no) and region. To ensure enrollment according to the intended distribution of screening blood eosinophil count, the number of participants in each stratification group will be controlled as follows:

- $\geq 300$  cells/mm $^3$ : approximately 15 participants per arm,
- $< 300$  cells/mm $^3$ : approximately 20 participants per arm.

In addition, in order to have an adequate number of participants with comorbid asthma, the number of participants without comorbid asthma will be limited to no more than 70% of the randomized population.

The study has a 24 to 52-week treatment period. Study treatment will stop for all participants when the last participant has completed 24 weeks of treatment. Therefore, all participants following protocol amendment 02 will be treated for at least 24 weeks and the other participants (enrolled before amendment 02) will have a variable treatment period which may be up to 52 weeks.

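### Health care use and missed days are totalled over treatment periods that run from 24 to 52 weeks by design, so the planned summaries have no fixed time base

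*SAP*

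**What the plan says.** SAP 3.7.1.4 covers health care resource utilization and productivity (HCRU). It sums health care use over the treatment period and treats absence the same way: the "cumulative number of missed days of school/work will be summarized over the treatment period". The output is simple: "Descriptive statistics (number of participants, mean, SD, median, minimum and maximum) will be provided". The section names no cut-off week, rate, person-time denominator or analysis population.

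The length of that period is set in SAP 1.1: "The study has a 24 to 52-week treatment period". It ends on a calendar rule: "Study treatment will stop for all participants when the last participant has completed 24 weeks of treatment". Protocol 4.1 says who is treated longer: "the other participants (enrolled before Amendment 02) will have variable treatment period and may continue up to 52 weeks". The SAP version history records that "The first participant was randomized on 24-Feb-2021", two years before Amendment 02 of 23 February 2023, so a mix of durations is to be expected.

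The questionnaires in Protocol 10.8.7 accumulate. The Week 12 form covers the time since treatment began, and the Week 24, 40 and 52 forms each cover the time since the previous form. The Week 40 form, for example, asks: "Since the last assessment of HCRU (about four months back), how many days did this patient miss from work". The later visits are not reached by everyone; footnote a of the Schedule of Activities states that "V6 and V7 are optional for participants given variable treatment period".

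**The concern.** Two participants with the same underlying burden can have very different totals because one entered the study earlier. Each further questionnaire adds another interval to the sum. A mean of such totals mixes participants followed for about half a year with participants followed for a full year. It is not burden per 24 weeks or per year, and it cannot be set beside a figure from another study. The SD and maximum have the same defect, because part of the spread is calendar time.

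The rest of the visible plan avoids this. The primary, secondary and other visible exploratory efficacy endpoints are fixed at Week 24 (SAP 3.2 to 3.4). For adverse events, SAP 3.6.2 provides rates per 100 participant-years if exposure is imbalanced between arms. SAP 3.7.1.4 has neither safeguard.

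**Working it through.** The documents give no expected count, rate or sample size for HCRU, so there is no plan figure to reproduce. The rates, the duration patterns and the spread between people are assumptions, shown as ranges.

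**Inputs from the documents.** Treatment period 24 to 52 weeks (SAP 1.1). About 15 participants per arm with eosinophils at or above 300 cells/mm³ and about 35 per arm overall (SAP 1.1 and 4). Both sizes are used because SAP 3.7.1.4 names no population.

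**1. Totals at equal burden.** Expected total = rate × weeks. The ratio is 52/24 = 2.17 at any rate.

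| Assumed missed days per 4 weeks | Total over 24 weeks | Total over 52 weeks |
|---|---|---|
| 0.5 | 3.0 | 6.5 |
| 1 | 6.0 | 13.0 |
| 2 | 12.0 | 26.0 |

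Equivalently, a rate lower by 1 − 24/52 = 54% over 52 weeks gives the same total as the full rate over 24 weeks.

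**2. Chance difference between arms in mean duration.** If durations are uniform on 24 to 52 weeks, the mean is 38 weeks and the SD is 28/√12 = 8.08 weeks. The standard error of the difference is SD × √(2/n).

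- n = 15 per arm: 8.08 × √(2/15) = 2.95 weeks (7.8% of 38).
- n = 35 per arm: 8.08 × √(2/35) = 1.93 weeks (5.1% of 38).

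The uniform pattern is an assumption. With duration = min(52, 24 + weeks between a participant's entry and the last entry), and entry uniform over 104 weeks, 76/104 = 73% of completers reach 52 weeks. The mean is then 48.2 weeks and the SD 7.5, and the standard errors are 2.74 and 1.79 weeks. If half were treated for 24 weeks and half for 52, the SD is 14 and they are 5.11 and 3.35 weeks. All of these ignore the stratified permuted blocks, which tend to balance entry date, so they are likely too high.

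**3. Share of the spread in totals that is due to duration.** For a Poisson count with rate r and duration T, independent of each other, the variance is E[r]E[T] + E[r]²Var(T) + Var(r)E[T²]. Take r = 0.25 per week and uniform durations. The Poisson term is 0.25 × 38 = 9.5, and the duration term is 0.0625 × 65.3 = 4.08.

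- Everyone has the same rate: 4.08/(9.5 + 4.08) = 30%.
- Rates vary with a coefficient of variation of 0.5: the third term is 0.0156 × 1509 = 23.6, and the share is 11%.
- Coefficient of variation of 1: the third term is 94.3, and the share is about 4%.

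Over rates of 0.5 to 4 days per 4 weeks, these shares become 18% to 63%, 9% to 14%, and about 4%.

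**4. After the change.** At 1 day per 4 weeks, totals to Week 24 are 6.0 and 6.0. As a rate, both participants have 13.0 days per 52 weeks.

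**The case against.** The strongest reply is that little turns on this. The endpoint is exploratory, SAP 3.7.1.4 plans no treatment difference, interval or test, and 1:1 blocked randomisation balances planned duration in expectation. That stands. It limits the severity, but it does not give the mean a time base.

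Second, SAP 3.1 promises summaries at each visit, and Table 10 in SAP 5.4 gives HCRU its own windows for Weeks 12, 24, 40 and 52. By-visit output would hold the Week 12 and Week 24 pieces. This helps in part, but the measure that the SAP specifies for HCRU is still the cumulative total.

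Third, the exploratory endpoint rows are blacked out in both documents, and a Week 24 limit could sit there. A reader should therefore not infer that the whole plan lacks a time base. What can be said is that the visible analysis text gives none.

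A reader might also infer that stopping study drug early cuts the count and so flatters an arm with more discontinuations. The documents do not support that. Footnote c of the Schedule of Activities and Protocol 7.1.1 ask participants who stop to complete the remaining visits and assessments, and the last HCRU window in Table 10 runs to the planned end-of-treatment date, not the last dose. Withdrawal from the study or missed visits would shorten the count; stopping drug alone should not.

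Finally, SAP 3.6.1 reports participant-years of drug exposure, from which a rate could be approximated. That denominator is based on dosing dates in the safety population, so it does not match the reporting time of someone who stops drug but keeps answering.

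**Conclusion.** The point holds at low severity. As visibly specified, HCRU totals are not standardised for time, and by design the time differs up to 2.17-fold between participants who complete treatment. That ratio needs only a burden that is constant over time; the 6 and 13 days also need the assumed rate.

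The main harm is to the meaning of the mean, SD and maximum. Chance imbalance between arms comes second, at a standard error of about 2 to 3 weeks under uniform durations (35 to 15 per arm, blocking ignored). It would be wrong to conclude that half of the variability is follow-up time: duration doubles the expected total just as rate does, but its share of the variance is well below half once participants differ much in their rates. The primary and secondary endpoints are unaffected.

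**What to change.** In SAP 3.7.1.4:

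- Make the main summary the cumulative totals from Day 1 to Week 24, formed from the Week 12 and Week 24 questionnaires. Their recall periods join without a gap, and both visits are scheduled for everyone. State how a missing form is handled.
- Add, as a second line, the rate per participant-year over the observed HCRU reporting period, up to the planned end of treatment or the last completed questionnaire, whichever is earlier.
- Name the analysis population and show reporting time by arm.

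The cost is SAP wording and a short derivation. No new data and no change to study conduct are needed. The one downside is that information after Week 24 enters only the rate.
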